Sleep disturbance may hinder the rehabilitation process. Clinically significant sleep disturbances after TBI correlate with higher rates of depression, anxiety, pain ([name] DJ, 2012) and fatigue (Englander J, 2010), all conditions which could deter full engagement in rehabilitation. Even in a healthy population a moderate reduction in the amount of quality sleep over time can negatively impact cognitive functions such as behavioral alertness and working memory (Banks S, 2007). BWL exposure has been shown to be effective in both reducing agitated behavior and improving cognition in older adults with dementia (Mishima K, 1994) (Riemersma-van der Lek RF, 2008) (Forbes D, 2011). After TBI, there is an association of sleep problems with more functional limitations, higher reliance on other people for care, and diminished satisfaction with quality of life at one year after injury ([name] DJ, 2012). Improved sleep in the acute recovery phase after TBI may positively impact other rehabilitation outcomes. In the study by Makley, et al. (Makley MJ J.-G. L., 2009) sleep disturbance was associated with longer average length of stay for both acute trauma center (22 days vs. 9 days) and inpatient rehabilitation (37 days vs. 21 days). In non-TBI populations BWL exposure has shown efficacy in the treatment of mood symptoms and improving alertness even with small doses and durations of treatment, such as a single one-hour session (Reeves GM, 2012) (Riemersma-van der Lek RF, 2008) (Revell VL, Jan 2006) (Chang AM, 2012) (Terman M, 2005) (Wirz-Justice A, 2012) (Friedman L, May 2012)

(Neikrug AB, 2012). These additional effects of BWL exposure may provide clinical benefit beyond improved sleep in persons recovering from TBI and will be assessed in the proposed study.

Research and clinical evaluation of sleep often employ actigraphy, which allows for the evaluation of subject movement over time and can be extrapolated to wake/rest cycles (Morgenthaler TI, 2007). Use of actigraphy for sleep evaluation with subjects after brain injury has been successful in both inpatient (Zollman FS C. C., 2010) and outpatient settings (Ayalon L, 2007). Additionally, considerations regarding movements and sleep specific to TBI and actigraph placement, including spasticity and paresis (Zollman FS C. C., 2010), are important and will be considered in the execution of this study.

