Aim 1: In persons with TBI, prospectively compare overnight sleep efficiency in a cohort exposed to morning Bright White Light with a comparison group exposed to Red Light in an acute inpatient rehabilitation setting.

Aim 2: Explore the relationship between Bright White Light exposure during inpatient rehabilitation after TBI and mood, therapy participation, attention, rate of functional recovery and length of stay.

Aim 3: Develop and describe sleep study procedures on the inpatient rehabilitation unit for persons with TBI to support optimal and feasible design of future studies in this important area.

Research Hypothesis:

In persons with TBI, prospectively compare overnight sleep in a cohort exposed to morning Bright White Light with a comparison group exposed to Red Light in an acute inpatient rehabilitation setting.

Hypothesis 1: Individuals exposed to Bright White Light for 30 minutes each morning will have better sleep compared to the Red Light exposure group, as measured by sleep efficiency.

Hypothesis 2: Individuals with daily morning Bright White Light exposure will have better mood (as measured by the Positive and Negative Affective Schedule, PANAS), therapy participation (as measured by a 0-100 therapist rating) and attention (as measured by the Symbol Digit Modalities Test) at 10 days compared to individuals with daily Red Light exposure. The group exposed to Bright White Light will also have less daytime sleepiness and fatigue (as measured by the Karolinska Sleepiness Scale (KSS) and the Barrow Neurological Institute Fatigue Scale (BNI-FS), a faster rate of functional recovery as measured by FIM™ efficiency for the rehabilitation stay and a shorter length of stay compared to those in the Red Light group

Hypothesis 3a: Bright White Light exposure will be rated as a reasonable addition to clinical care by staff using Likert scale ratings. Categorize and quantify rates of any side effects of Bright White Light and Red Light exposure in persons with TBI during inpatient rehabilitation.

Hypothesis 3b: Bright White Light and Red Light exposure will be generally well tolerated with side effect profiles and rates similar to those observed in previous studies with other populations.

[figure not shown]
See Appendix for Flowchart on Specific Aims of this study

V. Study Description

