We propose to recruit a prospective cohort of persons with TBI to compare effects of Bright White Light exposure to Red Light (RL) exposure. Light therapy treatments will be given daily in the morning for up to 10 days, and an Actiwatch will be worn that records movements for the entirety of the study. We will utilize objective assessments of sleep quality, subjective mood report, rate sleepiness and fatigue and complete measures of attention and participation in rehabilitation therapies to explore the

effects of light exposure in the acute inpatient rehabilitation setting. We will also evaluate the anticipated device costs and staff burden involved in utilizing light therapy exposure in the inpatient rehabilitation clinical setting. An overview of study procedures with timeline is described in Figure 1 below with further details in the sections that follow.

Figure 1. Overview of Study Procedures for TWILIGHT

VI. Screening for Eligibility:

Although subjects will be screened for this study concurrent with screening for eligibility for enrollment into the Traumatic Brain Injury Model System (TBIMS) study (Traumatic Brain Injury Model Systems, 2013), these are independent studies and subjects will have the choice to enroll in both, neither, or either one. The TBI Model Systems program, sponsored by the National Institute on Disability and Rehabilitation Research (NIDRR), is the largest longitudinal study of TBI in the nation. NIDRR awards 5 year grant awards to institutions that are national leaders in medical research and patient care and these. Institutions which receive this distinction are collectively termed, the TBI Model Systems. As part of the TBI Model Systems, the University of Washington TBI Model Systems research team is recognized as providing the highest level of comprehensive specialty services from the point of injury through chronic care stages, including re-entry into full community life. The current grant cycle is for the 2012-2017 time period, and one of the areas of interest for the UW TBI Model Systems research team is the treatment of sleep difficulties after TBI.

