The screening process will begin will reviewing the medical charts for patients that are on the inpatient rehabilitation unit at Harborview Medical Center. If a patient meets the inclusion criteria, research staff will approach the patient to determine whether the patient is cognitively capable of giving their consent for the study by administering the Galveston Orientation and Amnesia Test. The study will then be explained to the patient; or if the patient is experiencing post traumatic amnesia, the study will be explained to the patient’s legally authorized representative. Consent will be obtained either from the patient or, if he or she is unable to provide informed consent, the patient’s legally authorized representative.

VII. Study Sample:

Study participants will be recruited from acute inpatient rehabilitation at three participating TBI Model Systems institutions (University of Washington, Mount Sinai, Baylor). Eligible participants will be within three months of sustaining a moderate to severe TBI (as defined by the TBI Model Systems (Traumatic Brain Injury Model Systems, 2013)), admitted to acute inpatient rehabilitation, English speaking, and aged 18-70 years. Exclusionary medical factors will be identified in the medical record and through interview during screening/baseline assessment. In a pilot study comparing the effects of BWL and RL exposure in a sample of subjects with chronic TBI, Cantor et al. (Cantor, et al., 2012) reported an effect size of 0.63 for sleep duration. Because this pilot study involved subjects in the chronic phase of TBI, who were living at home rather than in an institution, and underwent a longer course of treatment (28 days in that study vs. 10 days in this study), we chose to take a conservative approach to calculating the required sample size. Based on an estimated effect size of 0.5 and 80% power, 128 subjects would be required to complete this study (64 per group). We anticipate recruitment over three years at three sites. Historical TBIMS and associated trial enrollment totals from the participating sites supports this study enrollment goal.

VIII. Inclusion Criteria:

1. Within three months of moderate to severe TBI
2. Admitted to acute inpatient rehabilitation
3. Ages 18-70
4. English speaking

VIII. Exclusion Criteria:

1. Complete blindness
2. Absence of eye opening or disorders of consciousness (Rancho level of 1-3)
3. Past medical history of retinal pathology
4. Past medical history of light sensitivity

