Day 0-1 (2 days): After determining eligibility, the participant will be fitted with an Actiwatch (actigraphy) for continuous monitoring of activity levels both during the day and night (American Sleep Disorders Association, 1995). The Actiwatch will be worn continuously (with removal as needed for hygiene, shower or other clinical care) from enrollment to outcome measurement. Actiwatches will be fully charged and cleared of all previous data before being provided to a subject. Units will be set to record activity data in 60-second epochs. Actiwatches have sufficient built-in memory capacity and battery life to be used for approximately 30 days without recharging. Additionally, sleep logs that rate patient sleep are filled out every hour, between the hours of 2200-0600, this information is then obtained

as completion of the Makley scale. A complete review of symptoms and medical history will be obtained from the subject, LAR, and medical records.

Day 2: Baseline data collection is obtained (See Appendix for Baseline Data Collection Forms). Measures collected include: Symbol Digit Modalities Test, Positive and Negative Affect Schedule (PANAS), Barrow Neurological Fatigue Scale. Clinical Staff, will be asked if there was sleep difficulties and therapist will be asked to rate therapy participation for that day.

Day 2: Randomization. After baseline testing is completed, subjects will be randomized (50:50) using a 2-level stratification design based on two pieces of information:

- 1) Center (U. Washington-Seattle, Baylor-Dallas, Mount Sinai-New York) and
- 2) Severity of Sleep Disturbance using Delirium Rating Scale-Revised 98 Item 1

The rating for the Delirium Rating Scale Item 1 are: 1=Mild, 2=Moderate, 3=Severe

(Nakase-Richardson R S. M., Prospective evaluation of the nature, course, and impact of acute sleep abnormality following TBI , 2013) Using an Access Database, developed by [name] at the University of Washington, centers will randomize the participant into either the Bright White Light Group or the Dim Red Light Group. [46]

Light Therapy:

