- 3) Clinical Staff feedback: phototherapy intervention will rated using a likert scale on the following categories:

- a. Ease of use
- b. Perceived relevance to rehabilitation care
- c. Impression of effectiveness.

Post Light Therapy Outcome Assessment

Day 13: At the conclusion of the light therapy sessions (and prior to discharge from rehabilitation), a blinded Outcomes Examiner will complete the post therapy outcome assessment. This assessment will include the following:

- Symbol Digit Modalities Test
- Positive and Negative Affect Schedule (PANAS)
- Barrow Neurological Fatigue Scale

XII. Data Analysis

The primary outcome is the between-group difference (BWL vs. RL exposure) in average sleep efficiency at baseline compared to after 10 days of light treatment. ANOVA will be used to compare groups controlling for demographics, injury severity, and use of medications.

Secondary outcomes (mood, therapy participation, attention, daytime sleepiness/fatigue) between groups assessed at baseline and after 10 days of light therapy will be compared using repeated measures ANOVA. FIMTM efficiency and inpatient rehabilitation length of stay will also be compared between groups using ANOVA controlling for the same variables as the primary outcome. Descriptive analysis will summarize responses to the nursing burden questions including estimated staff time for the intervention.

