There is no compensation planned for subjects who choose to participate in this study.

XXI. Overall Project Evaluation

Overall study data completeness, timeliness, and quality will be monitored by the study investigators. Automated data reports will be generated monthly, displaying information relevant to the milestones described in the previous section. For example, cumulative subject accrual rates, subject retention rates, inter-rater reliability, and data accuracy reports will be generated routinely to monitor progress toward goals. Progress toward study milestone will be discussed at the project meetings. Quarterly reports will be filed with the NIDRR project officer. Quarterly safety reports will be submitted to [name]. Annual reports will be filed with the TBIMS Annual Reports.

Investigators and key study personnel will meet by telephone bi-weekly prior to the initiation of the intervention to discuss progress. Investigators will meet twice yearly at the TBIMS Project Directors meeting. Site teams will meet weekly during the intervention period to discuss progress and barriers. If problems arise or tasks are not progressing as planned, [name] will work with the research team to devise an action plan. Plans will be put in writing with a timeline to correct the problem. [name] will track and follow-up on these plans. Any significant problems that would affect overall project outcomes will be reviewed with the NIDRR project officer to obtain additional assistance in developing an action plan.

Table 3: Timeline of Research Activities

	2013	2014	2015	2016	2017
Pre-Enrollment Activities					
Complete feasibility study	X				
Manual of Procedures	X				
Primary site IRB	X				
Collaborator sites IRB		X			
Research Assistant Training		X			
Rehab Staff Training		X			
Post-Enrollment Activities					
Cumulative Enrollment Target			43	86	128
Data collection		X	X	X	X
Actigraphy interpretation		X	X	X	X
Data Analysis/Dissemination					
Primary study report					X
Manuscript preparation					X

Figure 2. Project Staff Flow Chart

List of Acronyms and Abbreviations

- **ACG** = Actigraphy
- **AE** = adverse event
- **BMI** = body mass index
- **BNI-FS** = Barrow Neurological Institute Fatigue Scale
- **BWL** = Bright white light (experimental treatment condition in this study)
- **DSM** = Data safety monitor
- **GCS** = Glasgow Coma Scale
- **GOAT** = Galveston Orientation and Amnesia Test
- **KSS** = Karolinska Sleepiness Scale

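### No criterion requires enough remaining rehabilitation stay to reach Day 13, and the plan does not say how patients discharged sooner enter the primary analysis

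*Combined protocol and SAP*

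**What the plan says.** **Eligibility.** Section VII (Study Sample) describes eligible patients as "admitted to acute inpatient rehabilitation", within three months of injury, English speaking and aged 18 to 70. The numbered inclusion list in Section VIII repeats this. None of the eleven exclusions, and no line of the appendix checklist, concerns expected discharge or how late in the stay a patient may be consented.

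**Schedule.** Section XI and Table 1 place baseline on Days 0 to 2, randomisation on Day 2 ("subjects will be randomized (50:50) using a 2-level stratification design"), light from Day 3, and outcomes on Day 13. The Day 13 visit is tied to the stay: "At the conclusion of the light therapy sessions (and prior to discharge from rehabilitation), a blinded Outcomes Examiner will complete the post therapy outcome assessment". No assessment after discharge is described.

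**Course length.** Section V says "Light therapy treatments will be given daily in the morning for up to 10 days". Section XI says that subjects will receive ten morning sessions.

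**Analysis.** Section XII defines the primary outcome as sleep efficiency at baseline compared with after 10 days of light. It gives no analysis population, no rule for early discharge and no method for a missing primary outcome. The only missing-data guidance concerns the nursing sleep logs.

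**Sample size.** Section VII: "Based on an estimated effect size of 0.5 and 80% power, 128 subjects would be required to complete this study (64 per group". In Table 3 the row "Cumulative Enrollment Target" runs 43, 86, 128.

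**Length of stay.** Section I cites a study with average stays in "inpatient rehabilitation (37 days vs. 21 days", the longer figure being for patients with sleep disturbance. Hypothesis 2 predicts "a shorter length of stay compared to those in the Red Light group".

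**The concern.** Reaching the Day 13 visit takes about 14 calendar days on the unit, counting the day of consent as Day 0. A patient whose discharge is already planned for a week after consent meets every criterion, is randomised, and leaves after a few sessions. As the plan is written, that patient has no sleep-efficiency value after 10 days of light and no Day 13 attention, mood, fatigue or participation score.

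Two things are at stake. The first is power: the enrolment target has no slack, so each such patient reduces it. The second is comparability. Patients who leave early may differ in sleep from those who stay, and the trial itself hypothesises that bright white light shortens stay. If that happened during the treatment days, the two sets of completers would no longer be fully comparable.

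**Working it through.** **1. Reproducing the plan's figure.** Inputs from Section VII: effect size 0.5, power 80%. Alpha and sidedness are not stated; I assume two-sided 0.05. A two-sample t-test (noncentral t) needs 63.77 per arm, rounded up to 64, or 128 in total, with power 80.1%. This matches the plan. One-sided 0.05 would give 50 per arm and does not match.

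**2. Attrition allowance.** 128 must complete and 128 is the enrolment target: 128/128 = 1, so the implied loss is zero.

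**3. Share leaving before Day 13.** The documents give a mean stay of 37 days for sleep-disturbed patients, but no spread and no usual day of consent. Assumptions: gamma-distributed stay with shape 1/CV² and scale 37 × CV²; CV 0.4 to 0.8; consent (Day 0) on stay day c = 3, 7 or 14; patient still present at randomisation on Day 2. With F the cumulative distribution,

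share = [F(c + 13) − F(c + 2)] / [1 − F(c + 2)].

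Example with CV 0.6 and c = 7: shape 2.78, scale 13.32, F(9) = 0.0452, F(20) = 0.2357. The share is 0.1905/0.9548 = 0.20.

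| CV | c = 3 | c = 7 | c = 14 |
|---|---|---|---|
| 0.4 | 4% | 10% | 24% |
| 0.6 | 15% | 20% | 27% |
| 0.8 | 22% | 24% | 27% |

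A lognormal stay with the same mean and CVs, and consent 0 to 7 days after admission, gives about 1% to 27%.

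**4. Power if early leavers contribute nothing.** Per-arm n = 64 × (1 − loss), effect size 0.5:

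| Loss | n per arm | Power | Enrolment for 128 completers, 128/(1 − loss) |
|---|---|---|---|
| 0% | 64 | 80.1% | 128 |
| 10% | 57.6 | 75.8% | 143 |
| 20% | 51.2 | 70.7% | 160 |

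**5. Could the loss differ by arm?** Hypothesis 2 gives no size. Suppose bright white light shortened stay by 10%, which is an assumption (multiply the gamma scale by 0.9). In the example above the share rises from 20.0% to 23.9%. For consent on stay day 3 or 7, across the three CVs, the difference between arms is about 2 to 4 percentage points. For day 14 it is about 3 to 7 (largest at CV 0.4: 23.6% to 30.9%). Applying the 10% to the whole stay is generous to the concern, because days before the first session cannot be affected.

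**6. Bias among completers.** Suppose discharge depends on a standard normal score with correlation r to sleep efficiency, and that better sleepers leave first. If a fraction L leaves an arm, the mean of those who remain falls by r × φ(z)/(1 − L), with z the (1 − L) normal quantile.

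- Loss of 20% under red light: 0.2800/0.80 = 0.350.
- Loss of 24% under bright white light: 0.3109/0.76 = 0.409.
- Difference: 0.059 × r. A true effect of 0.50 becomes 0.48 at r = 0.3 and 0.47 at r = 0.5.

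Wider gaps (10% loss under red light, 15% to 20% under bright white light) give 0.42 to 0.48. With equal loss, or with r = 0, the estimate stays at 0.50.

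**The case against.** The strongest reply is that this is mainly a gap in the analysis plan, and that admitting every inpatient is a defensible pragmatic choice for a trial that also studies feasibility. Several parts of that reply stand.

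- A reader might infer that Hypothesis 2 makes the loss arm-dependent. It does not follow. A discharge date foreseeable at consent precedes randomisation and is balanced in expectation. Only stay shortened by treatment within the treatment days can differ by arm, and neither its size nor its timing is given.
- A reader might infer that these patients are lost to the primary outcome altogether. The Actiwatch is worn from enrolment (Section XI) and the software reports each night (Section XII), so treated nights exist up to discharge. FIM and length of stay are recorded at discharge and are not lost. What is missing is a rule saying whether those nights count.
- A reader might apply the 21-day mean, which under the gamma model, counting from presence at consent, gives losses of 30% to 73%. That mean belongs to patients without sleep disturbance, and Section IX says that patients with normal sleep will not be enrolled. The checklist exception is a zero rating with recent sleep medication.
- Consent as late as stay day 14 may be uncommon. Section II limits the target population to 30 days from injury, and Section I cites 22 acute-care days with sleep disturbance, which leaves 30 − 22 = 8 rehabilitation days on average. The operative lists, however, allow three months.
- A minimum-stay criterion cannot prevent discharge hastened by treatment, and it restricts the range of two secondary outcomes.

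None of this supplies the missing handling rule or an allowance for loss.

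**Conclusion.** The gap is real and should be closed, but it is moderate and of uncertain size. Followed as written, the plan can randomise patients who cannot supply the endpoint as defined, and the stated 80% power holds only if all 128 enrolled patients complete. About 4% to 27% leaving before Day 13 is a reasonable range, with 20% at CV 0.6 and consent on stay day 7. It rests on one cited mean and on an assumed distribution, spread and consent day. The power figures assume that early leavers contribute no data and are therefore the pessimistic end.

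Differential loss is a possibility, not a consequence of the design. Under an assumed 10% shorter stay it is a few percentage points, and the resulting bias is a modest attenuation that vanishes if discharge is unrelated to sleep.

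**What to change.** 1. **Section XII.** Keep every randomised patient in the primary analysis, using the treated actigraphy nights recorded up to discharge or Day 13. State how a patient with no treated night is handled, and report early discharges by arm. Reconcile the Section V wording on course length with the ten sessions in Section XI. This also covers discharge hastened by treatment. The cost is interpretive: the estimate becomes the effect of assignment over the nights available, and short courses may dilute it. No new data are needed.
2. **Section VIII and the checklist.** Add that the treating team's projected rehabilitation discharge is at least 14 days after consent, recorded before randomisation. Because it is applied before allocation, it cannot bias the arms, and it needs no added procedure or staff. It costs somewhat more screening per randomised patient, limits the population to those expected to stay long enough for the course, and restricts the range of length of stay and FIM efficiency.
3. **Section VII.** State that the 80% power is conditional on 128 completers, and give the power expected at 128 enrolled under a stated loss rate. This costs a sentence.

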XVII. Ethical Considerations/Protection of Human Subjects

Ethical Conduct of the Study

This study is to be conducted according to US and international standards of Good Clinical Practice (FDA Title 21 part 312 and International Conference on Harmonization guidelines), applicable government regulations and Institutional research policies and procedures.

Institutional Review Board (IRB)

This protocol and any amendments will be submitted to a properly constituted Institutional Review Board (IRB), in agreement with local legal prescriptions, for formal approval of the study conduct. The decision of the IRB concerning the conduct of the study will be made in writing to the investigator.

Subject Information and Informed Consent

This study will be conducted in compliance with Title 45 Part 46 of the CFR pertaining to informed consent. At the first visit, subjects will give their written consent to participate in the study after having been informed about the nature and purpose of the study, participation/termination conditions, risks, and potential benefits. Informed consent is a process that is initiated prior to the individual's or proxy's agreeing to participate in the study and continuing throughout the individual's study participation. Extensive discussion of risks and possible benefits of this therapy will be provided to the participants and their families. Consent forms describing in detail the Study Agent(s)/Intervention(s) study procedures and risks are given to the participant/proxy and written documentation of informed consent is required prior to starting study agent/intervention. Consent forms will be IRB approved and the participant/proxy will be asked to read and review the document. Upon reviewing the document, the investigator will explain the research study to the participant/proxy and answer any questions that may arise. The participants/proxies should have sufficient opportunity to discuss the study and process the information in the consent process prior to agreeing to participate. The participants/proxies may withdraw consent at any time throughout the course of the study. A copy of the informed consent document will be given to the participants/proxies for their records. The rights and welfare of the participants will be protected by emphasizing to them that the quality of their medical care will not be adversely affected if they decline to participate in this study.

Sample Characteristics that Raise Special Concerns

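### Section VII needs 128 completers for 80% power, but 128 is also the final enrolment target and no allowance for loss is stated

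*Combined protocol and SAP*

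**What the plan says.** Section VII starts from the stated design values, "Based on an estimated effect size of 0.5 and 80% power", and concludes that "128 subjects would be required to complete this study (64 per group"). Allocation is equal: in Section XI, "subjects will be randomized (50:50"). Alpha and sidedness are not given.

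Two sentences after the sample-size figure, Section VII says: "Historical TBIMS and associated trial enrollment totals from the participating sites supports this study enrollment goal". The only trial size in that section is 128. In Section XXI, the Table 3 row "Cumulative Enrollment Target" reads 43, 86 and 128 for 2015, 2016 and 2017.

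On loss, Section XVII says: "The participants/proxies may withdraw consent at any time throughout the course of the study". Section XXI lists "cumulative subject accrual rates, subject retention rates" among the items to be reported routinely. No expected or tolerated loss rate appears.

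On the analysis, Section XII says: "ANOVA will be used to compare groups controlling for demographics, injury severity, and use of medications". It gives no R-squared and no method for missing outcomes.

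**The concern.** A requirement on completers and a target for enrolment can be the same number only if nobody is lost. Here they are the same number, and nothing in the plan argues that loss will be nil. The three annual targets are the thirds of 128 rounded up (128/3 = 42.7, 256/3 = 85.3), so the completer figure seems to have gone into the recruitment timeline unchanged.

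The plan itself treats enrolment and completion as different things. Table 2 in Section XIII tracks monthly enrolment separately from completion of baseline, intervention and outcome assessments. Some loss is foreseeable from the design: consent can be withdrawn, and the outcome visit is on Day 13 and must come before discharge.

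What is at stake is how the result is read. If the trial enrols to Table 3 and finds no difference, readers will judge that result against 80% power, when the number analysed may have supported somewhat less.

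**Working it through.** **Inputs from the documents.** Effect size d = 0.5 and power 80% (Section VII); 64 per group, 128 in total (Section VII); 1:1 allocation (Section XI); final enrolment 128 (Table 3).

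**Assumptions.** Two-sided alpha of 0.05, a two-sample t-test, and loss falling equally on the two groups. The loss rates of 5% to 20% are also assumed, because the documents give none.

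**Step 1: reproduce 128.** The noncentrality parameter is d × √(n/2) with 2n − 2 degrees of freedom, where n is the number per group.
- Solving for 80% power at d = 0.5 gives n = 63.77, so 64 per group and 128 in total. This matches the plan exactly.
- With one-sided 0.05 the answer is n = 50.15, so 51 per group and 102 in total. That does not match, which supports the two-sided reading.

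**Step 2: the margin at 128.**

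| Completers per group | Power at d = 0.5 |
|---|---|
| 64 and 64 | 80.1% |
| 64 and 63 | 79.8% |
| 63 and 63 | 79.5% |

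The only slack is the rounding from 63.77 up to 64.

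**Step 3: enrol 128 and lose a fraction L.** Completers per group are 64 × (1 − L). The detectable effect is the d that gives 80% power at that n.

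| Assumed loss | Per group | Total | Power at d = 0.5 | Effect detectable with 80% power |
|---|---|---|---|---|
| 0% | 64.0 | 128.0 | 80.1% | 0.50 |
| 5% | 60.8 | 121.6 | 78.1% | 0.51 |
| 10% | 57.6 | 115.2 | 75.8% | 0.53 |
| 15% | 54.4 | 108.8 | 73.4% | 0.54 |
| 20% | 51.2 | 102.4 | 70.7% | 0.56 |

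A whole-number check at 10% loss, with 57 and 58 completers, gives 75.7% power and a detectable effect of 0.53.

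**Step 4: what covariate adjustment would have to supply.** If covariates explain a share R² of the outcome variance, the effective standardised effect is d/√(1 − R²). Setting power to 80% at the reduced n, and ignoring the degrees of freedom spent on covariates, gives:

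| Assumed loss | R² needed |
|---|---|
| 5% | 0.047 |
| 10% | 0.098 |
| 15% | 0.149 |
| 20% | 0.200 |

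**Step 5: enrolment that would keep 128 completers.** 128/(1 − L), rounded up, is 135, 143, 151 and 160 at 5%, 10%, 15% and 20% loss.

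**The case against.** The best opposing case has four parts.

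- **The wording may not mean completers.** The sentence could be read as saying that 128 subjects are needed to carry the study out, which fits the later mention of an enrolment goal. This is a strained reading of a requirement for subjects to complete the study. Even if it is accepted, the missing allowance for loss remains.
- **The effect size was already conservative.** Section VII cuts a pilot effect of 0.63 to 0.5, and at d = 0.63 a 20% loss from 128 still leaves about 88% power. But the cut is explained by the chronic phase, home setting and longer treatment of the pilot, and the 0.63 was for sleep duration. None of it was set aside for attrition.
- **Loss should be small.** Participants are inpatients, outcomes are taken on Day 13, and the study cited in Section I had mean rehabilitation stays of 37 days with disturbed sleep and 21 days without. Actigraphy is also summarised night by night, so a partial course may still give data. This stands as a reason to expect the lower rows of the range to apply rather than 15% or 20%. It does not make loss zero, and the plan does not state the low rate it would justify.
- **The analysis is adjusted, so true power may be higher.** This also stands in part. An R² of 0.05 to 0.10 would offset a 5% to 10% loss. But Section VII claims no such gain, and no R² is given, so a reader cannot tell whether it would be reached.

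It is also fair to say that nothing is miscalculated: 128 is right for the inputs given. The fault lies in using it for two different quantities.

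**Conclusion.** The concern holds. The stated 80% power belongs to 128 completers, the plan enrols 128, and no allowance connects the two. On the unadjusted calculation that reproduces the plan's figure, power is below 80% as soon as one subject is lost. The size is modest: about 2 points at 5% loss, 4 at 10%, 7 at 15% and 9 at 20%, with the detectable effect rising from 0.50 to at most 0.56.

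This rests on two-sided alpha of 0.05, inferred because it reproduces 128, and on assumed loss rates spread evenly over the groups. Power under the adjusted analysis could be higher, but the documents do not allow it to be calculated. The point should be corrected, but it does not threaten the design.

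**What to change.** Revise Section VII so that it states alpha and sidedness, 128 as the number enrolled, the expected loss, the resulting evaluable number and the power at that number. As an example, an assumed 10% loss leaves about 115 evaluable subjects, 76% power at d = 0.5, and a detectable effect of 0.53 at 80% power.

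If 80% is to be kept through covariate or baseline adjustment, say so and give the assumed R² or correlation. At 10% loss this is an R² of about 0.10, a correlation of about 0.31 (√0.098).

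Label the Table 3 row explicitly as enrolled or completed so that it agrees with Section VII. If the sponsor intends 128 completers, a separate and larger enrolment figure is needed; Step 5 of the working gives the range.

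With 128 kept as the enrolment figure, the cost is protocol wording only and no extra patients. The downside is that the stated power becomes slightly less favourable unless the adjustment is justified.
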